7.2.2 Safety Analyses from Randomization through All of Follow-up

The analyses described in Section 7.2.1 above will be performed again for the entire duration of the study.

7.2.3 Statistical Analysis of Adverse Events

AEs will be analyzed according to the body system described in the *CIT-TCAE* manual. Any event that appears in a body system will be categorized into one of the five severity grades according to the *CIT-TCAE* manual or the general definition of severity given in Table 2 and analyzed accordingly. For each event, we will analyze its incidence rate per 100 person-days. Suppose for each subject, the incidence of a particular event is a Poisson process with the homogeneous incidence rate λ . At the time of analysis, if a subject is only followed r days after the randomization, the incidence of this event is distributed according to the Poisson distribution with mean $r\lambda/100$. The maximum likelihood estimate of the incidence rate will be obtained based on data collected from the available subjects at the analysis time. The 95% confidence interval derived using the maximum likelihood estimator theory will be also reported.

8 Interim Analyses

The DSMB will be convened to review safety and efficacy data following National Institutes of Health (NIH) policy. When requested, formal interim analyses to assess safety and efficacy will be performed. Formal interim analyses will include distributions of endpoints, biomarkers, and AEs. Additional analyses may be requested by the DSMB.

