3.1 Study Period

The study period of this trial is a 24-month follow-up visit after the final islet transplant. Subjects may undergo up to 3 transplants in the course of this study; the final transplant must occur not later than 8 months following the first transplant.

In the first period, individuals who meet the general inclusion criteria will be approached regarding participation in the study. After informed consent has been obtained, they will be formally enrolled into the study. Eligibility will be confirmed based on the results of the screening visit procedures detailed in the study Schedule of Events (Appendix 1 of the CIT-02 protocol). Enrolled subjects who meet the eligibility screening for the studies will be put on the waiting list for an islet transplant.

Once a compatible islet preparation becomes available, a subject's eligibility will be reconfirmed, and eligible subjects who are randomized to Protocol CIT-02 will begin immunosuppression therapy on Day 0 (Day 0 is defined as the day of transplant).

During the post-transplant follow-up period, subjects may receive up to two additional transplants. After receiving his/her initial islet transplant, if a subject does not meet the criteria for insulin independence described in the Study Definitions section of the CIT-02 protocol, but has either a basal or stimulated C-peptide level ≥ 0.3 ng/mL (0.1 nmol/L), s/he will be considered for a second islet transplant. A second islet transplant will be

considered after day 85, but before 8 months after the first islet transplant and when all required metabolic assessments are complete. If, after the second islet transplant, both basal and stimulated C-peptide levels remain <0.3 ng/mL (0.1 nmol/L), the recipient will be considered to have failed the endpoint, and immunosuppression will be managed as described in the protocol. A third islet transplant will be considered only if all the criteria described in Section 7.6.2 of the CIT-02 protocol are met. Islet transplant recipients who have completed 8 months of follow up after their first infusion will no longer be eligible for additional islet transplants under the CIT-02 protocol. The number of excluded subjects and the number of protocol violations will be noted throughout the duration of the study.

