7.2 Analysis of Secondary Endpoints for Safety Endpoints

The secondary safety endpoints described in Section 4.1.2.2 of the CIT-02 protocol target AEs related to islet transplantation (transplant procedure and/or islet product) and the immunosuppression and/or infection prophylaxis.

The targeted AEs related to the islet transplantation include:

- 1. AE-IP-1: Bleeding (>2 g/dL decrease in hemoglobin concentration)
- 2. AE-IP-2: Segmental portal vein thrombosis
- 3. AE-IP-3: Biliary puncture
- 4. AE-IP-4: Wound complication (infection or subsequent hernia)
- 5. AE-IP-5: Increased transaminase levels (>5 times ULN)

The targeted AEs related to the immunosuppression or infection prophylaxis therapy or related to the secondary investigational agent include:

- 1. AE-IIP-1: Allergy
- 2. AE-IIP-2: Reduction in GFR
- 3. AE-IIP-3: Increase in urinary albumin excretion
- 4. AE-IIP-4: Addition or intensification of anti-hypertensive therapy
- 5. AE-IIP-5: Addition or intensification of anti-hyperlipidemic therapy
- 6. AE-IIP-6: Oral ulcers

- 7. AE-IIP-7: Lower extremity edema
- 8. AE-IIP-8: Gastrointestinal toxicity
- 9. AE-IIP-9: Neutropenia, Anemia, or Thrombocytopenia
- 10. AE-IIP-10: Viral, Bacterial, or Fungal Infections
- 11. AE-IIP-11: Benign or Malignant Neoplasms

Other safety endpoints include:

- Incidence of the change in the immunosuppression drug regimen
- Incidence of immune sensitization defined by the presence of anti-HLA antibodies absent prior to transplantation

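### The procedure-type adverse events (AE-IP-1 to AE-IP-5) get a rate per 100 person-days but none per transplant, so the rate moves with transplant count and follow-up at unchanged procedural risk

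*SAP*

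**What the plan says.** Section 7.2.3 sets one rate for all adverse events: "For each event, we will analyze its incidence rate per 100 person-days". The model is "Suppose for each subject, the incidence of a particular event is a Poisson process with the homogeneous incidence rate" λ, and exposure is calendar time: "At the time of analysis, if a subject is only followed r days after the randomization", the expected count is rλ/100. No class of event is exempted.

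Section 7.2 lists five targeted events tied to the islet transplantation, AE-IP-1 to AE-IP-5, for example "AE-IP-2: Segmental portal vein thrombosis". It gives them no denominator of their own.

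On exposure to the procedure, section 3.1 says "Subjects may undergo up to 3 transplants in the course of this study". A second transplant is "considered after day 85, but before 8 months after the first islet transplant", and the last must fall within the same eight months. On follow-up, the same section says "The study period of this trial is a 24-month follow-up visit after the final islet transplant".

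Section 7.2.1 reports incidence rates by event type and severity from randomization to Day 365 after the first transplant, without defining the denominator. Section 7.2.2 adds: "The analyses described in Section 7.2.1 above will be performed again for the entire duration of the study". No section gives an adverse event rate per transplant or per infusion.

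**The concern.** For an event such as a biliary puncture, the natural unit of exposure is one transplant procedure. The numerator grows with the number of infusions. The denominator in section 7.2.3 grows with days since randomization, nearly all of them free of any procedure. A constant daily hazard is therefore a poor description of these five events, and the model-based confidence interval inherits the misfit.

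Two things follow. Subjects or cohorts with the same risk per procedure show different rates if they differ in number of transplants. The rate for a given cohort also drifts down between successive analyses merely because time has passed, which matters for a rate computed on whatever follow-up exists at the analysis time. Subjects who start immunosuppression but are never transplanted belong to the safety population (section 3.3.3) and add person-days with no procedure.

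What is lost is a prespecified estimate of the risk per procedure, which a monitoring board or a later trial would want for these events.

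**Working it through.** The SAP states no adverse event rate, so there is no figure to reproduce. The check applies the SAP's own model.

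**Inputs**
- Rate: 100 × events / person-days (section 7.2.3, maximum likelihood under the stated Poisson model).
- Transplants per subject: k = 1, 2 or 3 (section 3.1).
- Second transplant after day 85, so day 86 at the earliest; last transplant within 8 months, taken as 244 days (section 3.1).
- Follow-up: 24 months, taken as 730 days, after the last transplant (section 3.1). Total days are 730 + L, where L is the day of the last transplant.
- Assumption: randomization is close to the day of the first transplant, so days are counted from there.
- Assumption: a constant risk q per procedure. The SAP gives none; q = 0.10 is used for illustration, with 0.05 and 0.20 as the range.
- Assumption: the rate of section 7.2.3 is applied to the windows of sections 7.2.1 and 7.2.2.

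**Formula.** Expected rate per 100 person-days = 100 × k × q / r, with r the days in the window.

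**Results for q = 0.10**

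| Transplants (day of last) | To Day 365 | All follow-up |
|---|---|---|
| 1 (day 0) | 10/365 = 0.0274 | 10/730 = 0.0137 |
| 2 (day 86) | 20/365 = 0.0548 | 20/816 = 0.0245 |
| 2 (day 244) | 20/365 = 0.0548 | 20/974 = 0.0205 |
| 3 (day 244) | 30/365 = 0.0822 | 30/974 = 0.0308 |

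With q = 0.05 every figure halves; with q = 0.20 it doubles. Per procedure, the answer is q in every row.

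**Ratios, three transplants against one (q cancels)**
- To Day 365: 3.
- All follow-up: (3/974) / (1/730) = 2190/974 = 2.25, with the third transplant at the latest permitted time. An earlier third transplant shortens follow-up and raises the ratio. Because it must come after a second transplant that is itself after day 85, the ratio stays below 2190/816 = 2.68.

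**Drift with follow-up, one transplant, q = 0.10.** At day 30: 10/30 = 0.333. At day 365: 0.0274. At day 730: 0.0137. The procedural risk is the same throughout.

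**A mixed cohort of 12.** Suppose six subjects have one transplant, four have two (last at day 160) and two have three (last at day 244). Procedures: 6 + 8 + 6 = 20; expected events 2.0. Person-days over all follow-up: 6 × 730 + 4 × 890 + 2 × 974 = 9,888. The rate is 200/9,888 = 0.0202, against 0.0137 if all 12 had one transplant, a ratio of 1.48. To Day 365 it is 200/4,380 = 0.0457 against 0.0274, a ratio of 20/12 = 1.67.

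**The case against.** Several counter-arguments are sound and limit the point.

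- **Other outputs exist.** Section 7 plans incidence summaries for serious, non-serious and all adverse events, and section 7.2.1 adds severity tables, resolution times and attribution of serious events. A reader might infer that adverse events are reported only per person-day; the SAP does not support that. None of these outputs is stated per procedure, however.
- **The windows and the unit stand in different sections.** Sections 7.2.1 and 7.2.2 do not mention person-days. For regimen change and sensitization, section 7.2.1 attaches an exact interval to the incidence rate, which is how section 6.1 treats a binomial proportion. The incidence rates there may therefore be proportions of subjects. The window-specific figures above are conditional on the other reading.
- **The extremes should not be crossed.** Setting 0.0822 (three transplants, Day 365) against 0.0137 (one transplant, all follow-up) gives a 6-fold contrast. It changes window and transplant count together, so it does not measure the effect of transplant count within a planned analysis. A pooled cohort also lies inside the same-window extremes.
- **Total burden is a legitimate measure.** Re-transplantation is considered when insulin independence is not reached (section 3.1), so it is partly a result of the regimen. A regimen that needs more infusions does expose subjects to more procedural harm, and a per-procedure figure alone would hide that.
- **Assignment to a procedure is not automatic.** Section 2.3.2.3 says these events are only generally thought to be procedure-related and that relatedness is captured for serious events only. A fall in hemoglobin, a transaminase rise or a late hernia may arise well after an infusion.
- **Reconstruction is partly possible.** The proportions receiving second and third transplants are reported, and with 12 subjects a reader could approximate the number of procedures. The monitoring board may also request further analyses.

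What survives is that the only rate defined for these five events uses a unit that does not fit them, and that no per-procedure figure is prespecified.

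**Conclusion.** The point holds as a low-cost improvement to the analysis; it is not an internal contradiction or a wrong figure. Section 7.2.3 applies a constant person-day rate to procedure-type events and the SAP plans no procedure denominator. At equal risk per procedure, the rate for three transplants against one differs 3-fold to Day 365. It differs 2.25-fold over all follow-up with the third transplant at eight months. The rate also falls as procedure-free time accrues.

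The ratios do not depend on the assumed risk. They do rest on events clustering at infusion, on randomization close to the first transplant, and on applying the section 7.2.3 rate to the section 7.2.1 and 7.2.2 windows. The absolute rates rest in addition on the illustrative 10%.

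A reader might infer that a stopping decision could be distorted, because section 8.1 compares all endpoints with the parallel CIT-07 study. The documents do not support this: the stopping recommendations in section 8.1 rest on the primary endpoint, and no rule uses an adverse event rate. A difference in procedural event rates between the two studies could still reflect re-transplantation rather than risk per procedure, so the comparison would be easier to read with both measures shown.

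**What to change.** In sections 7.2.1 to 7.2.3, for AE-IP-1 to AE-IP-5:

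1. Add a table of procedures followed by the event within a prespecified analysis window after that infusion, divided by procedures performed, separately for first and later transplants. Fix the window for each event type before the data are reviewed, and list events outside it separately.
2. Give a confidence interval that allows for repeated procedures in one subject. For first transplants there is one procedure per subject, so an exact binomial interval applies directly; later or pooled transplants need an interval with the subject as the cluster.
3. Show the proportion of subjects with at least one event, with an exact confidence interval, so that total burden including re-transplants stays visible. State whether the incidence rates of section 7.2.1 are already meant as this proportion.
4. Keep the rate per 100 person-days for non-procedural events.

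The cost is SAP wording and one extra table built from event and transplant dates. The downsides are that a window must be chosen for assigning events, and that subjects with several transplants count more than once in the per-procedure figure. With 12 subjects the later-transplant rows will be imprecise.

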8.1 Interim Analyses for Early Stopping

During the period when CIT is enrolling, CIT-02 will enroll at half the rate. CIT-02 will be continuously monitored with a futility analysis, and a recommendation for stopping new enrollment will be made if the accruing information indicates that the primary endpoint of CIT-02 is unlikely to be meaningfully higher than the historical rate of 15-20%; "meaningfully higher" is taken to be 50%.

As each CIT-02 endpoint is determined, an upper bound for the probability of a favorable CIT-02 primary endpoint will be calculated from an exact one-sided 95% confidence interval. A recommendation will be made to stop enrollment in CIT-02 if, and when, the upper bound is below 50%. Operationally, the following rule results:

Stopping Rule

- Stop at 5 subjects if there are no successes in first 5 subjects.
- Stop at 8 subjects if there is only 1 success in first 8 subjects.
- Stop at 11 subjects if there are 2 or fewer successes in first 11 subjects.
- Otherwise, complete enrollment to 12 subjects.

The rule ensures that, should 12 subjects be enrolled, there will be at least 3 successes out of 12 on the primary endpoint.

Should enrollment in CIT-02 be stopped, then long term follow-up data will continue to be collected until the end of the study.

An additional interim analysis will also be done for the DSMB at the time that CIT-07 enrollment is complete. In this analysis, all endpoints of CIT-02 are compared to corresponding endpoints of UM and UIC CIT-07 subjects. If the primary endpoint in CIT-02 has a significantly lower rate of favorable outcome using a one-sided test with a Type 1 error of 0.05, then a recommendation to stop enrollment in CIT-02 will be made.

Probability of	Probability	Probability	Probability	Probability
Event	Stop at 5	Stop at 8	Stop at 11	Reach 12
	Subjects	Subjects	Subjects	Subjects
0.1	0.59049	0.23915	0.09685	0.07350
0.2	0.32768	0.20972	0.13421	0.32838
0.3	0.16807	0.12353	0.09079	0.61760
0.4	0.07776	0.05599	0.04031	0.82594
0.5	0.03125	0.01953	0.01220	0.93701
0.6	0.01024	0.00492	0.00235	0.98248
0.7	0.00243	0.00077	0.00024	0.99656
0.8	0.00032	0.00005	0.00001	0.99962
0.9	0.00001	0.00000	0.00000	0.99998

 Table 3: Operating characteristics of stopping rule

References

